study from the Mayo Clinic,¹³ the distribution of MRE stiffness score in the adult Fontan population was $4,900 \pm 1,100$ Pa. Assuming that the standard deviation of MRE is 1,000 both for before and after treatment measures, and that the within subject correlation between before and after measures is at least moderate in strength and positive (i.e. $\rho \geq 0.5$), then the variance in the difference between pre- and post-treatment MRE stiffness score is no more than 250 Pa. A sample of 40 patients in the treatment arm will provide 80% power for a two-sided two-sample t-test with a 0.05 Type I error rate to detect a mean difference of at least 500 Pa in treatment effect, as measured by the difference within patient MRE stiffness score.

Interim Analysis

An interim analysis of subjects who have completed 12 months of Sildenafil vs. Placebo therapy will be conducted at the end of the grant period (August 2019). Those still on Sildenafil vs. Placebo at that time will remain blinded until their completion of 12 months on Sildenafil vs. Placebo.

I. Human studies issues (consent or research authorization)

Consent

An informed consent will be obtained from the patients at the time of enrollment in the study. The consent will authorize a member of the research team to contact each patient by phone, email, or questionnaire. The study participants will be notified of the very limited evidence supporting the use of sildenafil in this population.

Data and Safety Monitoring

The Food and Drug Administration approved Sildenafil for the treatment of pulmonary hypertension. The patients will be notified that the use of sildenafil in this study is off-label. We will implement an internal safety monitoring system consisting of two members (not immediately affiliated with the study) to review reported side effects of sildenafil at the mid-point and completion of the study. Finally, and as always, extreme caution and monitoring of study participants will be undertaken throughout the study and in follow up to ensure no untoward events as a direct result of the study substance. Please see data safety monitoring plan.

M. Literature cited

1. Fontan F and Baudet E. Surgical repair of tricuspid atresia. *Thorax*. 1971;26:240-8.
2. Rychik J. Forty years of the Fontan operation: a failed strategy. *Seminars in thoracic and cardiovascular surgery Pediatric cardiac surgery annual*. 2010;13:96-100.
3. Gewillig M. The Fontan circulation. *Heart*. 2005;91:839-46.

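### Section H assumes an MRE SD of 1,000 Pa without a reason, although its only cited source gives 1,100 Pa; this overstates power, and is secondary to the variance and arm-size errors in the same paragraph

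*Combined protocol and SAP*

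**What the plan says.** All of this is in section H, under Sample size and power.

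- **Source of variability.** The figure of 4,900 ± 1,100 Pa comes from a prior study at the same centre and is introduced with the words "the distribution of MRE stiffness score in the adult Fontan population was". No other figure for the spread of MRE stiffness appears in the documents.
- **Planning SD.** The next sentence begins "Assuming that the standard deviation of MRE is 1,000 both for before and after treatment measures". It gives no reason for going below the cited value.
- **Correlation.** The plan supposes that "the within subject correlation between before and after measures is at least moderate in strength and positive", with 0.5 as the lower bound. No data are cited for it.
- **Variance of change.** It concludes that "the variance in the difference between pre- and post-treatment MRE stiffness score is no more than 250 Pa".
- **Power.** The target is "to detect a mean difference of at least 500 Pa in treatment effect". The plan claims 80% power for this, using a two-sample t-test at a two-sided 0.05 level, and ties the claim to 40 patients on treatment. The paragraph opens, however, with 40 completers in total, 20 per arm.

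**The concern.** The planning SD is lower than the only estimate the plan offers, the change favours the study, and the reader is not told why. Eligibility does not supply the reason. Section G admits adult Fontan patients in general who can have MRI. None of its exclusions is defined by liver stiffness, and the plan does not argue that they narrow the spread.

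The variance of change scales with the square of the SD, so the effect carries through to power, sample size and detectable difference. It also survives repair of the paragraph's other errors. Someone who corrected only the variance formula and the arm size would keep 1,000 Pa and find that 64 per arm gives 80% power. At the cited SD those 64 per arm give 72.3%.

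**Working it through.** **Inputs (section H).** SD s = 1,000 Pa (assumed) or 1,100 Pa (cited, ± read as an SD); correlation ρ = 0.5, the plan's lower bound; difference between arms in mean change Δ = 500 Pa; two-sided α = 0.05; two-sample t-test; n = 20 per arm (opening sentence) or 40 per arm (the power sentence, with 1:1 allocation from section G).

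**Formulas.** Variance of change = 2s²(1 − ρ), with SD of change σ its square root. Power comes from the noncentral t distribution with 2n − 2 degrees of freedom and noncentrality Δ / (σ√(2/n)).

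**Step 1: the plan's own figure.** With s = 1,000 and ρ = 0.5, the variance of change is 2 × 1,000² × 0.5 = 1,000,000 Pa², so σ = 1,000 Pa. The stated 250 does not follow.
- 20 per arm: noncentrality 500 / (1,000 × √0.1) = 1.58; power 33.8%.
- 40 per arm: noncentrality 500 / (1,000 × √0.05) = 2.24; power 59.8%.

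The stated 80% is not reproduced. Other readings of 250 do not recover it either. A variance of 250,000 Pa² (σ = 500 Pa) gives 86.9% at 20 per arm and 83.0% at 18 per arm (20 less 10% attrition). An SD of change of 250 Pa gives more than 99.9%. Two combinations do give 80.0%: a paired test in 40 patients with σ = 1,100 Pa, and 20 per arm with σ = 550 Pa. Neither is the stated test with the stated inputs.

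**Step 2: the cited SD.** With s = 1,100 and ρ = 0.5, the variance of change is 2 × 1,100² × 0.5 = 1,210,000 Pa², so σ = 1,100 Pa.
- Ratio of variances: 1,210,000 / 1,000,000 = 1.21 (the same at any fixed ρ). The assumed variance is therefore 1 − 1/1.21 = 17.4% too low.
- 20 per arm: noncentrality 1.58 / 1.1 = 1.44; power 28.9%, a fall of 5.0 points (unrounded).
- 40 per arm: noncentrality 2.24 / 1.1 = 2.03; power 51.9%, a fall of 7.9 points.
- Number per arm for 80% power: 64 becomes 77.

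**Step 3: range over ρ at 20 per arm.** The difference detectable with 80% power is 0.909 × σ, because at σ = 1,000 Pa it is 909 Pa and it scales with σ.

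| ρ | σ, s = 1,000 | Power | Detectable | σ, s = 1,100 | Power | Detectable |
|---|---|---|---|---|---|---|
| 0.5 | 1,000 | 33.8% | 909 Pa | 1,100 | 28.9% | 1,000 Pa |
| 0.7 | 775 | 51.2% | 704 Pa | 852 | 44.0% | 775 Pa |
| 0.8 | 632 | 68.3% | 575 Pa | 696 | 60.1% | 632 Pa |
| 0.875 | 500 | 86.9% | 455 Pa | 550 | 80.0% | 500 Pa |

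**Step 4: offset by correlation.** SD 1,100 gives the same σ as SD 1,000 with ρ = 0.5 when 2 × 1,210,000 × (1 − ρ) = 1,000,000, that is, at ρ = 1 − 1/2.42 = 0.587.

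**The case against.** The strongest reply is that 1,000 Pa is openly an assumption, about 9% below a cited estimate that is itself uncertain. The source's sample size is not given in the plan. Under normality, a 95% interval around an SD of 1,100 has a lower limit of 919 Pa with 50 patients and 966 Pa with 100, and would include 1,000 for up to about 190 patients. The exclusions in section G (severe ventricular dysfunction, severe valve regurgitation, Fontan obstruction, viral hepatitis, severe renal dysfunction) could trim the extremes. The plan also treats 0.5 as a lower bound for the correlation, and 0.587 would cancel the effect. Moving the correlation from 0.5 to 0.7 at SD 1,000 changes power by 17 points (33.8% to 51.2%), the SD by only 5.

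Most of this stands as a limit on weight. This step is an unexplained input, not a miscalculation, and 1,000 Pa could be defended. But the plan does not make that defence. It cites no data for the correlation, and at whatever correlation is chosen the factor of 1.21 remains.

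A reader might infer that the SD lowers the stated 80% to somewhere between 72% and 75%, or that it explains why 80% cannot be reproduced. The documents support neither: with SD 1,000 the plan's inputs already give only 33.8% or 59.8%. A reader might also infer that a null result will necessarily be over-read. That does not follow, because a confidence interval at analysis uses the observed SD.

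**Conclusion.** The mismatch is real and unexplained, and it makes power too favourable at any fixed correlation. At ρ = 0.5 the size is 5.0 points at 20 per arm and 7.9 points at 40 per arm, from starting values well below 80%. The detectable difference at 20 per arm rises by about 10%.

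It is a secondary fault. The stated variance of 250, where the inputs give 1,000,000 Pa², and the conflict between 20 per arm and 40 in the treatment arm do far more damage. With either SD, the design at ρ = 0.5 does not deliver the stated power for 500 Pa.

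The figures rest on three assumptions: the unlabelled ± is an SD, the SD is equal at both time points as the plan assumes, and 20 per arm means completers. If 20 per arm is before attrition, 18 per arm remain and the fall at ρ = 0.5 is 4.5 points. Even on the most generous reading of the variance (250,000 Pa², equivalent to ρ = 0.875), 18 per arm gives 83.0% with SD 1,000 and 75.5% with SD 1,100, so the choice of SD can decide whether the target is met.

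**What to change.** In section H, as one correction of the paragraph:

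1. Use the cited 1,100 Pa at both time points, or state the reason for 1,000 Pa. Say whether the ± in the source is an SD.
2. Recompute the variance of change as 2s²(1 − ρ), and state one sample size per arm.
3. Restate, for the two-sample comparison at the planned 20 per arm, the power for 500 Pa and the difference detectable with 80% power. At ρ = 0.5 the detectable difference is about 1,000 Pa with SD 1,100 and 909 Pa with SD 1,000.
4. Show these over a range of ρ, such as the table above, because no correlation data are cited.

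The cost is one input and a few restated figures. Enrolment need not change. The only downside is a less favourable stated power.

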 6. Sildenafil will be initiated at 5 mg 3 times per day for the first week, and titrated to 10 mg 3 times per day for the second week and 20 mg 3 times per day from the 3rd week to the end of the study period. The patients will be required to check their pulse rate and blood pressure daily during the first month of drug therapy. Patient who experience hypotension (blood pressure < 90/50 plus symptoms such as dizziness) during dose titration will be asked to remain on the previous tolerated dose. Patients who cannot tolerate 10 mg 3 times daily will be asked to withdraw from the study and will be asked to

- continue checking their blood pressure for three days after stopping the medication.
7. After 12 months (+/- 4 weeks) of therapy, all tests listed in #3 and #4 will be repeated.
 8. These same tests listed in #3 and #4 will be repeated for the patients who have follow-up up to 24 months (+/- 4 weeks).
 9. Adverse event and compliance monitoring: During the first month of enrollment (initiation and dose titration), adverse events will be collected by subject report and by weekly telephone or email interview (± 7 days) with dedicated research personnel. For the rest of the study period, adverse events will be collected by subject report and by monthly telephone or email interview (± 14 days) with dedicated research personnel. The research personnel will be responsible for sending out the monthly supply of medications and obtaining a count of the remaining number pills as a measure of compliance. All participants will be provided with a pamphlet containing all the side effects of sildenafil, and contact information of research team for reporting any adverse event or concerns about the study.
Up to three voicemail messages will be left for each follow-up.

H. Statistical analysis and power considerations:

Sample size and power

We have determined that a total of 40 patients who complete the study (20 patients in the treatment arm and 20 patients in the placebo) will adequately power the study accounting for approximately a 10% attrition rate. In a prior

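### The sample size rests on a wrong variance: the plan's own inputs give an SD of change of 1,000 Pa, so 20 per arm has about 34% power for 500 Pa, not 80%

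*Combined protocol and SAP*

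**What the plan says.** All the statements are in section H of the combined protocol and SAP, under Sample size and power.

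- Size: "a total of 40 patients who complete the study (20 patients in the treatment arm and 20 patients in the placebo"). The text adds that this "will adequately power the study accounting for approximately a 10% attrition rate".
- Variability: "the standard deviation of MRE is 1,000 both for before and after treatment measures", with a before–after correlation of at least 0.5. The earlier cohort that the section cites had a mean of 4,900 Pa and an SD of 1,100 Pa.
- Derived variance: "the variance in the difference between pre- and post-treatment MRE stiffness score is no more than 250 Pa".
- Power claim: "A sample of 40 patients in the treatment arm will provide 80% power for a two-sided two-sample t-test". The significance level is 5%, and the target is a 500 Pa difference between the arms in mean within-patient change.

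Section G, item 5, sets 1:1 randomisation to sildenafil or placebo.

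**The concern.** The variance does not follow from the SD and correlation given in the same sentence, and pascals cannot be the unit of a variance of a stiffness in pascals. The power claim depends on that variance. It is also tied to an arm size of 40, although the preceding sentences put 20 in each arm.

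This paragraph is the only justification given for the size of the trial. If the true power is far below 80%, a reader who trusts the stated figure could take a non-significant result as evidence against a 500 Pa effect that the trial was unlikely to detect. Section H gives no other guidance on how to read such a result.

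**Working it through.** **Inputs, all from section H except allocation (section G, item 5).** SD 1,000 Pa at each time point; correlation ρ ≥ 0.5; between-arm difference in mean change 500 Pa; two-sided α = 0.05; two-sample t-test; 20 per arm, 1:1.

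**Step 1: the variance.** For a change score with equal SDs,

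Var(post − pre) = SD² + SD² − 2ρ·SD² = 2·SD²·(1 − ρ).

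At ρ = 0.5 this is 2 × 1,000² × 0.5 = 1,000,000 Pa², so the SD of change is 1,000 Pa. Because ρ = 0.5 is the lowest value allowed, this is the upper bound that the plan's sentence was meant to give. The stated 250 is smaller by a factor of 1,000,000 / 250 = 4,000.

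**Step 2: trying to reproduce the plan's 80%.** Power below is from the exact noncentral t distribution, for 500 Pa.

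| Reading | SD of change (Pa) | Patients | Power |
|---|---|---|---|
| 250 as a variance | 15.8 | 20 per arm | about 100% |
| 250 as an SD | 250 | 20 per arm | about 100% |
| 250,000 Pa² (thousands dropped) | 500 | 20 per arm | 87% |
| 250,000 Pa² | 500 | 18 per arm | 83% |
| Stated SD, ρ = 0.5 | 1,000 | 20 per arm | 33.8% |
| Stated SD, ρ = 0.5 | 1,000 | 40 per arm | 59.8% |
| Stated SD, ρ = 0.5 | 1,000 | 40 v 20 | 43.5% |
| Cited cohort's SD of 1,100, ρ = 0.5 | 1,100 | 20 per arm | 29% |

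The 250,000 Pa² rows come closest, but 2 × 1,000² × (1 − ρ) = 250,000 requires ρ = 0.875. At ρ = 0.5, none of the 20-per-arm or 40-per-arm readings gives 80% with the named test. Changing the analysis does not recover it either. A one-sided test gives 46% at 20 per arm and 72% at 40 per arm. Adjusting for baseline by ANCOVA (residual SD 1,000 × √(1 − 0.5²) = 866 Pa) gives 43% at 20 per arm.

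**Step 3: the corrected calculation at ρ = 0.5.** The noncentrality is 500 / (1,000 × √(2/20)) = 1.58 on 38 degrees of freedom, which gives the 33.8%. For the sample size, the normal approximation is n = 2 × (1.96 + 0.84)² × (1,000/500)² ≈ 63 per arm. The t-test needs 64 per arm, or 128 completers. With 20 per arm, 80% power is reached for a standardised difference of 0.909, which is 909 Pa.

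**Step 4: sensitivity to the correlation** (SD 1,000 Pa at each time point).

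| ρ | Variance (Pa²) | Power, 20 per arm | Power, 40 per arm |
|---|---|---|---|
| 0.5 | 1,000,000 | 34% | 60% |
| 0.6 | 800,000 | 41% | 69% |
| 0.7 | 600,000 | 51% | 81% |
| 0.8 | 400,000 | 68% | 94% |
| 0.85 | 300,000 | 80% | 98% |

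For 80% power at 20 per arm, the SD of change must be no more than 550 Pa, which means ρ of about 0.85. At 40 per arm it must be no more than 788 Pa, ρ of about 0.69.

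**Step 5: attrition.** If 40 is the number of completers, 10% attrition means about 40 / 0.9 = 44.4, so 45 enrolled. If 40 is the number enrolled, 36 complete (18 per arm) and power at ρ = 0.5 is 30.8%.

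**The case against.** The strongest reply is that the plan gives an inequality. Since ρ may exceed 0.5, 34% is the minimum power under the stated SD, not a fixed property of the design, and a correlation of 0.85 or more is compatible with the assumption and delivers 80%. That is correct, and the 34% should always be quoted with its condition. It does not rescue the claim. The plan sizes the trial on the bound, describes the correlation only as at least moderate, and gives no data supporting a value near 0.85.

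A second reply is that the authors may have used a different calculation. A one-sample paired t-test with an SD of change of 1,000 Pa has 87% power at n = 40 and 83% at n = 36, and the synopsis in section E describes only MRE before sildenafil and after 12 months. This fits the figure of 40 about as well as a variance of 250,000 Pa² does, so the origin of 250 and of 40 cannot be settled from the documents. But a one-sample test is not the test named and does not compare sildenafil with placebo.

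Third, the attrition wording is ambiguous, not contradictory. Forty completers with more enrolled is a natural reading, and the 18-per-arm figure is a secondary scenario. That stands. The conflict between 20 and 40 in the treatment arm remains.

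Finally, the type I error rate and the randomised comparison are unaffected, and how readers would take a null result is a prediction. Both points are fair, but neither makes the stated power correct.

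**Conclusion.** The concern holds. From the plan's own inputs the variance of the change is up to 1,000,000 Pa² (SD 1,000 Pa), not 250. At that bound, 20 completers per arm gives about 34% power for 500 Pa, so a true effect of that size would be missed about two times in three. Reading the arm size as 40 gives about 60%.

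These figures assume SD 1,000 Pa at both time points, ρ = 0.5, equal arms and the named two-sample t-test on change. A higher correlation raises the power, to 80% at about 0.85 with 20 per arm. The cited cohort's SD of 1,100 Pa lowers it to about 29% at ρ = 0.5. The paragraph must be corrected because it is the trial's only sample-size justification.

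**What to change.** Rewrite the paragraph in section H:

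1. State that with ρ ≥ 0.5 the variance of the change is at most 1,000,000 Pa² (SD 1,000 Pa).
2. State the power for the actual size: 20 completers per arm gives about 34% power for 500 Pa at ρ = 0.5, or 80% power for about 909 Pa. If a correlation of 0.85 or more is to be assumed instead, state it and justify it with data.
3. Replace the 40 in the treatment arm with 20 per arm.
4. Say whether 40 is the number randomised or the number completing, and give the other number under 10% attrition.
5. State that a non-significant result will be interpreted through the confidence interval for the between-arm difference, and not as evidence that a 500 Pa effect is absent. At an SD of change of 1,000 Pa and 20 per arm, the 95% interval extends about 2.02 × 1,000 × √(2/20) ≈ 640 Pa either side of the estimate, so even an estimate of zero would not exclude 500 Pa.

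The cost is one reworded paragraph and a less favourable power statement. It asks for no extra patients and no change to trial conduct.

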The use of pulmonary vasodilators will promote forward flow in the Fontan circuit, reduce hepatic congestion and halt the progression of liver fibrosis.

C. Innovation

(i) Available data suggest that chronic hepatic congestion, inherent in the Fontan physiology, is the precursor of early liver fibrosis and cirrhosis in the Fontan population.^{2,3} A recent study based on the Mayo Clinic Fontan

cohort showed that half of the patients had liver fibrosis after 30 years from the time of initial Fontan.⁶

(ii) This proposed study would be the first study to assess the role of pulmonary vasodilators in the management of FALD.

D. Significance

(i) The adult congenital heart disease program at Mayo Clinic has the largest and oldest cohort of Fontan patients in the United States, and this places Mayo Clinic in a unique position to study this problem.

(ii) Data from this study will influence the management of FALD nationally and worldwide.

E. Brief Synopsis of Methods

(i) All patients enrolled in the study will undergo a baseline liver magnetic resonance elastography (MRE) prior to the initiation of phosphodiesterase-5 inhibitor (sildenafil).

(ii) A second MRE will be performed after 12 months of therapy.

F. Preliminary studies to support feasibility

(i) Several studies have shown that the use of pulmonary vasodilators in Fontan patients (even those with normal pulmonary vascular resistance) results in increased cardiac output and exercise tolerance by promoting forward flow in the Fontan circuit.¹⁴⁻¹⁶

(ii) A recent study from the Mayo Clinic showed that liver stiffness measured by MRE correlates with severity of fibrosis on liver biopsy.¹³

(iii) The proposed study is built on the foundation of these previous studies. Pulmonary vasodilators will be used to promote forward flow in the Fontan

circuit, and thereby reduce liver congestion. MRE will then be used to monitor treatment effect. We chose a phosphodiesterase-5 inhibitor instead of an endothelin receptor antagonist because the latter is associated with hepatotoxicity.

G. Study design

1. Inclusion criteria: All adult (age \geq 18 years old) Fontan patients who have no contraindications for magnetic resonance imaging (MRI) will be eligible for the study. Informed consent will be obtained from potential participants by their primary cardiologist or dedicated study personnel.

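### The only efficacy test named is an unadjusted t-test on change in MRE stiffness; adding baseline MRE as a covariate would cut its variance by about 23% at a correlation of 0.5, falling to 4% at 0.875 (20 per arm)

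*Combined protocol and SAP*

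**What the plan says.** Section H has a sample-size paragraph and an interim paragraph, and neither designates a primary analysis. The one efficacy test appears in the power statement: "A sample of 40 patients in the treatment arm will provide 80% power for a two-sided two-sample t-test" at a 0.05 error rate, "to detect a mean difference of at least 500 Pa in treatment effect, as measured by the difference within patient MRE stiffness score". The other planning inputs are an SD of 1,000 Pa before and after treatment, and the assumption that "the within subject correlation between before and after measures is at least moderate in strength and positive" (rho of 0.5 or more). From these the plan concludes that "the variance in the difference between pre- and post-treatment MRE stiffness score is no more than 250 Pa". The same section gives the number of completers as "20 patients in the treatment arm and 20 patients in the placebo".

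No baseline covariate is mentioned anywhere. Section E plans a baseline MRE for everyone enrolled and a second at 12 months, Section G item 4a lists MRE among the baseline tests, and item 7 says that "all tests listed in #3 and #4 will be repeated" at 12 months. On the interim, Section H says "An interim analysis of subjects who have completed 12 months of Sildenafil vs. Placebo therapy will be conducted" in August 2019, but it names no test or model.

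**The concern.** The covariate most likely to predict 12-month stiffness is measured in every patient, and the named test does not use it efficiently. Subtracting baseline in full is the best use of it only when the regression slope of follow-up on baseline is 1. Under the plan's equal SDs that slope is rho, so subtracting the whole baseline value adds noise whenever rho is below 1. In a trial of 20 per arm the loss is worth recovering.

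There is a second, smaller issue. Because no primary analysis is declared, the choice between a change-score and a baseline-adjusted comparison is still open when the arms are compared at the interim, and the two can give different p-values.

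**Working it through.** **Inputs.** From Section H: SD 1,000 Pa at both times, rho at least 0.5, difference 500 Pa, two-sided 0.05, 20 completers per arm. From Section G item 5: 1:1 allocation. The plan does not state rho 0.875. It is the value at which SD 1,000 gives a change variance of 250,000 Pa², since 2(1 − 0.875) × 1,000² = 250,000. It applies if the printed 250 was meant as 250,000 Pa², which is an assumption.

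**The plan's own figure.** The variance of a change is 2(1 − rho)SD². At rho 0.5 it is 2 × 0.5 × 1,000² = 1,000,000 Pa², an SD of 1,000 Pa. Noncentral-t power for 500 Pa is then 33.8% at 20 per arm and 59.8% at 40 per arm. The stated 80% is not reproduced at rho 0.5. With a change variance of 250,000 Pa² (SD 500 Pa), power at 20 per arm is 86.9%.

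**Variance with and without adjustment, n per arm.**

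- Change score: 2(1 − rho)SD² × 2/n, with 2n − 2 degrees of freedom.
- Baseline-adjusted: (1 − rho²)SD² × 2/n × [1 + 1/(2n − 4)], with 2n − 3 degrees of freedom. The bracket is the average cost of estimating the slope.
- Ratio, adjusted to change: (1 + rho)/2 × [1 + 1/(2n − 4)].

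At n = 20 the bracket is 1 + 1/36 = 37/36. For rho 0.5 the ratio is 0.75 × 37/36 = 0.771. For rho 0.875 it is 0.9375 × 37/36 = 0.964.

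| rho | Variance ratio, 20 per arm | Cut | Power for 500 Pa, change → adjusted | Per arm for 80% power, change vs adjusted |
|---|---|---|---|---|
| 0.5 | 0.771 | 23% | 34% → 42% | 64 vs 49 |
| 0.7 | 0.874 | 13% | 51% → 57% | 39 vs 34 |
| 0.8 | 0.925 | 7.5% | 68% → 72% | 27 vs 25 |
| 0.875 | 0.964 | 4% | 87% → 88% | 17 vs 17 |

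**If 40 per arm was meant.** The power sentence puts 40 patients in the treatment arm and gives no placebo number. Taking 40 in each arm is an inference from 1:1 allocation, and it conflicts with the 20 and 20 given earlier. On that reading the ratios are 0.760, 0.861, 0.912 and 0.950 for the four values of rho. Power moves from 60% to 72%, 81% to 87%, 94% to 96%, and stays above 99%.

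**Simulation check.** With 20 per arm, bivariate normal data, equal SDs and 200,000 trials per setting, the variance ratio was 0.771 at rho 0.5 and 0.964 at rho 0.875. Power was 33.7% against 41.8%, and 87.0% against 88.1%.

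**Two analyses, one dataset.** In 40,000 simulated trials per setting at 20 per arm, with a true 500 Pa difference and rho 0.5, the two analyses disagreed on significance in 17% of trials. With no true effect each kept about 5% error, but taking the smaller of the two p-values gave 7.3%.

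**The case against.** The strongest reply is that this is a refinement, not an error. The t-test on change is valid and unbiased, and the plan gives its outcome, alpha and sidedness. All of that is correct, and the point claims only a loss of efficiency.

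The 23% is also the largest gain within the plan's range, because rho is assumed to be at least 0.5 and the documents give no estimate of it. At 0.875, the reading closest to the plan's own power claim, adjustment buys about one point of power. That stands too, and is why the range is shown.

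The figures depend on equal SDs. If the follow-up SD were 10% larger than baseline (an assumption, 20 per arm), the net variance ratio would be 0.84, 0.95, 0.995 and 1.02 at rho 0.5, 0.7, 0.8 and 0.875. At 20% larger it would be 0.90, 0.99, 1.02 and 1.02. So at high rho the gain can vanish or become a loss of up to about 2.5%, the cost of estimating the slope. A smaller follow-up SD would enlarge the gain. Equal SDs are the plan's own assumption, and the possible loss is small beside the possible gain.

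Finally, the open choice of analysis could be closed by declaring the t-test already named. That is true: pre-specification alone does not favour adjustment. The efficiency argument does.

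**Conclusion.** The concern holds. The plan names only an unadjusted comparison of change scores and does not use a covariate it already collects to best effect. Under its own equal-SD assumption, with a linear relation between baseline and follow-up, adjustment cuts variance by 23% at rho 0.5 and 4% at rho 0.875 with 20 per arm. At rho 0.5 that is worth 64 − 49 = 15 patients per arm at 80% power; at 0.875 it saves none. Adjusted power is never below that of the change score at any tabulated rho.

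This is a loss of efficiency and a gap in pre-specification, not a bias. Adjustment does not bring power to 80% at 20 per arm and rho 0.5: it reaches 42%. The change variance and the conflicting sample sizes in Section H need correcting in their own right.

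**What to change.** Add to Section H a single primary analysis: a linear model of 12-month MRE stiffness (Pa) on randomised arm, with baseline MRE stiffness as a continuous covariate, tested two-sided at 0.05 and reported as the adjusted mean difference with its 95% confidence interval. Keep the two-sample t-test on change as a sensitivity analysis. Fix this before any unblinded comparison, including the August 2019 interim, and use the same model at the interim and at the end.

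The cost is one sentence, one degree of freedom, and about 1/(2n − 4) of extra variance for estimating the slope: 1/36 = 2.8% at 20 per arm, or 1/76 = 1.3% at 40. That cost is already included in the figures above. No additional data are required, and no patient who could enter the change-score analysis is lost.
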